3.3.1. Study design

The proposed study is an observational, parallel group, non-randomized study in lactating mothers. It will be carried out at the University and Polytechnic Hospital La Fe (HULAFE), beginning at Month 21. Previously, the study protocol will be approved by the Ethics Committee for Biomedical Research of the Health Research Institute La Fe (Valencia, Spain) and the study participants will sign a relevant consent form. All procedures regarding volunteers' recruitment and participation, data security and handling will be in absolute accordance with the principles set under WP 9, concerning Ethical Requirements, and more specifically stated on Tasks 7.1 and 7.2 and D 7.2.

To address the objectives mentioned above, three mother-infant groups will be examined. In specific:

- Group A will consist of 25 pre-term infants fed with OMM (PT-OMM) and their mothers.
- Group B will consist of 25 pre-term infants fed with pasteurized DHM (PT-DHM), in range of complete enteral nutrition (150 mL/kg/day), and their mothers.
- Group C will consist of 25 full term infants receiving OMM (FT-OMM) and their mothers.

The study will be divided into two phases:

- A baseline phase, referring to the period between the time of delivery and the time preterm infants receive complete enteral nutrition (CEN) and full term infants recover of birth weight (RBW). During this period, all infants and their mothers will be evaluated, as described in the next section.
- 2. **An observational phase**, lasting six months and referring to the period that infants are fed with HMand/or formulas orsolid foods. During this period, assessments, as described below,

[figure not shown]

will be arranged for all mother-infants dyad and the donors providing the DHM in the hospital or the participants' home.

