3.3.2. Participants

Participants will be recruited in HULAFE. Visits at baseline, when preterm infants receive complete enteral nutrition (CEN; i.e. 150 mL/kg/day) and at months 1, 3, and 6 will be held at the hospital. Visits when full term infants recover of birth weight and at month 2 will be held at the participant's home.

The eligibility criteria for participating will be as follows:

Inclusion criteria

- Mother accepts to participate in the study and signs an informed consent form
- Gestational age < 32 weeks for the group of preterm infants and gestational age > 37 weeks for the full-term infants
- Exclusive consumption (i.e. >80% of intake) of OMM or DHM

Exclusion criteria:

- Mother requires special diet (e.g. celiac disease, diabetes)
- Mother consuming probiotics
- Infant needs intestinal surgery
- Severe congenital malformations
- Chromosomopathies

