Weight and height of mothers of the PT-OMM, PT-DHM, and FT-OMM will be measured. Weight will be measured on a levelled platform scale to the nearest 0.5 kg and height on wall-mounted stadiometer, to the nearest 0.5 cm. Body Mass Index (BMI) (kg/m²) will be calculated by dividing the weight in kilograms by the height in meters squared.

All infants will be evaluated regarding their growth by measuring weight, length and cranial perimeter upon every visit at the hospital. Weight and recumbent length will be measured on an electronic baby scale and on a neonatometer scale, to the nearest 0.5 kg and 0.5 cm respectively and cranial perimeter will be measured using a flexible inch tape to the nearest 0.5 cm.

Medical history assessment

At observational phase PT-OMM, PT-DHM and FT-OMM mothers' medical history, i.e. all the chronic conditions that they may have as well as the use of medicines, will be recorded.

Genotype characterisation

A buccal swap sample will be collected from mothers of PT-OMM, PT-DHM and FT-OMM at baseline. In specific, standard buccal swab kits will be used to gather DNA sample. Furthermore, umbilical cord

blood will be extracted from PT-OMM, PT-DHM, and FT-OMM newborns. The detailed protocol is described in Deliverable 3.1.

Metabolomecharacterisation

For the characterization of metabolic profile urine samples will be collected from mothers of PT-OMM, PT-DHM and FT-OMM and their infants, as described in Deliverables 2.2 and 3.1.

Microbiome assessment

Fecal samples from all mothers and their infants will be collected for studying the microbiome. The protocol followed is described in Deliverable 2.1.

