3.3.4.1. Measurements

Measurements concern sociodemographic information, dietary and other lifestyle behaviors, anthropometry, medical history, genotype, metabolome, and microbiome.

Dietary assessment

Upon every visit of the observational phase mothers of PT-OMM, PT-DHM, and FT-OMM as well as donors providing the DHM will complete a validated semi-quantitative food frequency questionnaire (FFQ) [35], from which MedDietScore, will be calculated [36], as described in section 3.3.3.

In addition, during the hospital visit at month 1 all mothers will be asked to return a 4-day food record, in which they will have recorded all foods and drinks consumed for three consecutive weekdays and one day of the weekend. Nutrients' intake will be calculated using the Nutritionist Pro™ Diet Analysis (Axxya Systems, Woodinville, WA, USA) software. The research team involved in the diet analysis is competent in using the proposed software, and HUA has a long history of analyzing dietary data through it. Another strength of the proposed software is that it comprises food databases from multiple countries, which can be used to extrapolate the most relevant and reliable reference. We aim to cross-match intake data, and compare the validity of the FFQ against the 4-day food record, in order for the most valid to be used in the platform.

Other lifestyle behaviors assessment

Physical activity levels of mothers of PT-OMM, FT-OMM and PT-OMM as well as milk donors providing DHM will be evaluated at every visit, as described in section 3.3.3.

Furthermore, the mothers will be asked regarding their smoking habits [38]. In specific current smoking status (yes/no), smoking frequency (1, daily; 2, less than daily; 3, not at all) and exposure to second hand smoking (yes/no) will be recorded.

[figure not shown]
Anthropometric assessment

Weight and height of mothers of the PT-OMM, PT-DHM, and FT-OMM, as well as milk donors providing DHM will be measured and recorded at every visit at the hospital, as described above.

All infants will be evaluated regarding their growth by measuring weight, length and cranial perimeter upon every visit at the hospital. Weight and recumbent length will be measured on an electronic baby scale and on a neonatometer scale, to the nearest 0.5 kg and 0.5 cm respectively and cranial perimeter will be measured using a flexible inch tape to the nearest 0.5 cm.

Medical history assessment

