3.3.5. Sample size

In order to achieve statistical power of at least 95% at 5% significance level of two-sided hypotheses for the evaluation of 10% standardized mean differences of fat and protein composition of HM, as well as growth markers (weight, height), and health status (number of gastrointestinal and respiratory diseases) of preterm infants, a total of 75 mother-infant dyads (25 per Group of Study II) will be enrolled.

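### Study II records infant weight only to the nearest 0.5 kg, which badly degrades early individual weight change and modestly degrades weight at a single early visit

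*Protocol*

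**What the plan says.** The resolution is fixed twice for infants. Protocol section 3.3.3.1 (baseline phase) has weight and recumbent length taken "on an electronic baby scale and on a neonatometer scale, to the nearest 0.5 kg and 0.5 cm respectively". Section 3.3.4.1 (observational phase) repeats it: "Weight and recumbent length will be measured on an electronic baby scale and on a neonatometer scale, to the nearest 0.5 kg and 0.5 cm". For mothers, section 3.3.3.1 says "Weight will be measured on a levelled platform scale to the nearest 0.5 kg", so adults and newborns share one figure. No finer infant resolution appears anywhere in the document. Sections 3.3.3 and 3.3.4 only point to operating procedures to come from WP3.

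The infants are defined in section 3.3.2: "Gestational age < 32 weeks for the group of preterm infants and gestational age > 37 weeks for the full-term infants". Infant growth is objective (c) in section 3.2. Section 3.3.6 lists weight among the dependent variables of the regressions on milk composition, and section 3.3.5 includes "growth markers (weight, height") among the measures behind the sample size. Section 3.3.1 ends the baseline phase at "the time preterm infants receive complete enteral nutrition (CEN) and full term infants recover of birth weight (RBW"). Infants are weighed at hospital visits, but section 3.3.2 places the visit for recovery of birth weight at the participant's home.

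**The concern.** A 0.5 kg step suits an adult on a platform scale. For an infant born before 32 weeks it is a large fraction of body weight, and for a term newborn it exceeds the weight normally lost and regained in the first days. Weight is a named growth outcome. Rounding happens when the reading is recorded, so no later analysis can restore what is lost. With 25 infants per group there is little information to spare. The changes most exposed are the short early ones, when infants are closest to exclusive human milk feeding.

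**Working it through.** The 0.5 kg figure is a specification, so the plan has no derived number to reproduce. The check is what that step does to the data.

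**Inputs from the protocol.** Step h = 0.5 kg (3.3.3.1, 3.3.4.1); 25 infants in each of two preterm groups, so n = 50 preterm (3.3.1).

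**Assumed inputs (the documents give none).** Preterm weight 1.2 kg, SD 0.3 (SD varied 0.25-0.40); early gain 0.2 kg with SD 0.10-0.15, or 0.4-0.5 kg with SD 0.15-0.20; term birth weight 3.3 kg, SD 0.45, with a 5-10% loss; SD 0.9 kg at month 6; true correlation of 0.5 between milk composition and the weight outcome.

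**1. Rounding error.**
- Maximum error: h/2 = 0.25 kg.
- SD for one weight: h/√12 = 0.5/3.464 = 0.144 kg.
- SD for a difference of two weights: h/√6 = 0.5/2.449 = 0.204 kg.
- Over assumed preterm weights of 0.75-1.75 kg, one step is 0.5/0.75 = 67% down to 0.5/1.75 = 29% of body weight.

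**2. Power formula.** With Fisher's z, power ≈ Φ(√(n−3)·atanh(r) − 1.96), where r is the true 0.5 multiplied by the correlation between recorded and true values. Those correlations come from simulating 400,000 infants rounded to 0.5 kg. Without rounding, √47 × 0.549 = 3.77, which gives 96%.

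**3. Weight at a single early visit (preterm).** Recorded weights take practically four values: 0.5, 1.0, 1.5 and 2.0 kg, in about 7%, 50%, 40% and 3% of infants. The mean absolute error is 11%. Recorded weight still correlates 0.90 with true weight, so r = 0.5 × 0.90 = 0.45 and power is about 91%. With SD 0.25-0.40 it is 89-94%.

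**4. Early weight change (preterm).**

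| Assumed gain (SD), kg | Correlation of recorded with true gain | Power |
|---|---|---|
| 0.2 (0.10) | 0.41 | 29% |
| 0.2 (0.15) | 0.58 | 53% |
| 0.4-0.5 (0.15-0.20) | 0.60-0.70 | 56-71% |

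In the two 0.2 kg rows, 58-60% of infants record exactly zero gain.

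**5. Term weight loss.** A loss of 5%, 7% or 10% of 3.3 kg is 0.165, 0.231 or 0.33 kg, always under one step. At the lowest weight, 67%, 54% and 34% of infants respectively would be recorded at their birth weight.

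**6. Month 6.** Extra variance is 0.144²/0.9² = 0.0208/0.81 = 2.6%.

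**The case against.** The strongest reply is that section 3.3.6 makes weight, not weight gain, the dependent variable. For weight itself the loss is modest: the correlation with true weight stays near 0.90 and power falls only from 96% to about 91%. That stands, and it sets the size of the finding for the analysis as written. The other outcomes under objective (c), namely length, cranial perimeter and disease counts, do not depend on the 0.5 kg figure.

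A reader might infer that early growth cannot be measured, or that objective (c) loses most of its information. The documents do not support that. Group means and growth over six months remain estimable with added noise, and month 6 is hardly touched.

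A reader might also infer that recovery of birth weight cannot be dated. That is not established either. The infant weighing rule covers hospital visits, the visit in question is at home, and it serves as a time point and not as an analysed outcome. What remains is conditional: the document gives no other weighing rule for that time point, and if the 0.5 kg resolution were used it would fail.

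The text calls itself a preliminary design and defers detailed procedures to WP3. Staff may read the scale more finely, and the figure may be a unit error or a carry-over from the mothers' scale, repeated in the second section. No data collection form is shown, so whether the figure reaches one is unknown. These points explain the slip but do not remove it: a procedure that follows the protocol inherits 0.5 kg, and one that does not contradicts it.

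Nothing here shows that the 0.5 cm resolution for length and cranial perimeter is inadequate, so no change to it is asked for.

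**Conclusion.** The point holds for infant weight. The rounding errors follow directly from the stated step, given a spread of weights that is wide relative to it. Individual early weight change is badly degraded; weight at a single early visit is modestly degraded; later visits are little affected. The power figures, the shares of infants with no recorded gain and the shares of term infants with no recorded loss rest on the assumed weights, gains, losses and SDs, and the power figures also on r = 0.5. They show scale and are not forecasts. Because the loss cannot be recovered once readings are rounded and costs almost nothing to prevent, the correction belongs before enrolment.

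**What to change.** In sections 3.3.3.1 and 3.3.4.1, replace the infant weight resolution with grams at the graduation of the electronic baby scale, for example the nearest 5-10 g. State that the same resolution applies to any weighing used to establish recovery of birth weight, including at home. Keep 0.5 kg for mothers only. Leave length and cranial perimeter as they are. Make sure that the WP3 procedures and the data field for infant weight use grams.

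The cost is wording in two sections and one field definition. The hospital scale and the visit schedule do not change; a weighing at home needs a scale that reads at this resolution.

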3.3.4. Observational Study Phase

[figure not shown]
A thorough evaluation of the health status of the mother-infant dyad and the donors providing the DHM will be performed, including dietary and other lifestyle parameters assessment, medical history and evaluation, anthropometric measurements and microbiome profiling. A description of each of these aspects follows. Evaluations in the donors providing the DHM will be performed every time a batch is donated. Detailed Standard Operating Procedures employed for sample collection, storage and outcome assessment will be provided in WP3. Results obtained from data analysis will be used to feed the NUTRISHIELD platform and train the NUTRISHIELD algorithm.

3.3.4.1. Measurements

Measurements concern sociodemographic information, dietary and other lifestyle behaviors, anthropometry, medical history, genotype, metabolome, and microbiome.

Dietary assessment

Upon every visit of the observational phase mothers of PT-OMM, PT-DHM, and FT-OMM as well as donors providing the DHM will complete a validated semi-quantitative food frequency questionnaire (FFQ) [35], from which MedDietScore, will be calculated [36], as described in section 3.3.3.

In addition, during the hospital visit at month 1 all mothers will be asked to return a 4-day food record, in which they will have recorded all foods and drinks consumed for three consecutive weekdays and one day of the weekend. Nutrients' intake will be calculated using the Nutritionist Pro™ Diet Analysis (Axxya Systems, Woodinville, WA, USA) software. The research team involved in the diet analysis is competent in using the proposed software, and HUA has a long history of analyzing dietary data through it. Another strength of the proposed software is that it comprises food databases from multiple countries, which can be used to extrapolate the most relevant and reliable reference. We aim to cross-match intake data, and compare the validity of the FFQ against the 4-day food record, in order for the most valid to be used in the platform.

Other lifestyle behaviors assessment

Physical activity levels of mothers of PT-OMM, FT-OMM and PT-OMM as well as milk donors providing DHM will be evaluated at every visit, as described in section 3.3.3.

Furthermore, the mothers will be asked regarding their smoking habits [38]. In specific current smoking status (yes/no), smoking frequency (1, daily; 2, less than daily; 3, not at all) and exposure to second hand smoking (yes/no) will be recorded.

[figure not shown]
Anthropometric assessment

Weight and height of mothers of the PT-OMM, PT-DHM, and FT-OMM, as well as milk donors providing DHM will be measured and recorded at every visit at the hospital, as described above.

All infants will be evaluated regarding their growth by measuring weight, length and cranial perimeter upon every visit at the hospital. Weight and recumbent length will be measured on an electronic baby scale and on a neonatometer scale, to the nearest 0.5 kg and 0.5 cm respectively and cranial perimeter will be measured using a flexible inch tape to the nearest 0.5 cm.

Medical history assessment

Number of respiratory, gastrointestinal, and neurologic infections, number of hospital admissions due to infectious diseases as well as antibiotics use will be recorded for infants of all three groups upon every visit.

o Metabolome characterisation

For the characterization of metabolic profile urine samples will be collected from mothers of PT-OMM, PT-DHM and FT-OMM and their infants at each evaluation, as described in Deliverables 2.2 and 3.1.

Human milk nutrient composition assessment

OMM will be collected at every visit. DHM aliquots of each milk batch will be collected before and after pasteurization and fortification of DHM will be recorded. The detailed protocol is described in Deliverable 2.3.

Microbiome assessment

OMM and DHM before pasteurization will be analyzed for microorganism's content. Fecal samples from mothers of PT-OMM, PT-DHM and FT-OMM and their infants will be also collected for studying the microbiome at every visit. The protocol followed is described in Deliverable 2.1.

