2.3.2. Participants

Participants will be recruited at the San Raffaele Hospital (OSR). All visits and blood and urine sample collection will be held at the hospital. Fecal sample collection (for microbiome analysis) will be performed at home.

Inclusion criteria

Children with obesity and/or diabetes, aged 8-18 years visiting hospital on an outpatient basis.

Exclusion criteria:

- Children with any acute or chronic disease (tumor, infection, others), gastrointestinal diseases, cardiovascular disease, chronic renal disease, diseases of the parathyroid, diseases necessitating regular phlebotomies, and other chronic diseases which could affect the results of the study
- Use of medicine which could affect the results of the study, such as systemic glucocorticoids,
 lipid-lowering or anti-hypertensive drugs
- Recent weight loss or weight gain (> 3 kg), within the previous 3 months of the beginning of the study
- o Transfusion of blood in the last three months before Study Phase I
- Use of dietary supplements, including multivitamins, fish oil capsules, minerals, and trace elements (three months before and during the entire study period)
- Inability (physically or psychologically) to comply with the procedures required by the protocol.

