Finally, intake of dietary supplements (e.g. vitamins) will be recorded and all children will be also asked whether they are medically diagnosed with dietary allergies or other diseases [1, lactose intolerance; 2, celiac disease; 3, medical diseases under restrictive dietary schemes (sub-question-please refer); 4, other (please refer)] and whether they follow a vegetarian (all sub-types) or vegan diet (yes/no). If the answer to the former question is positive they will be asked for further details [1, vegan; 2, lacto-vegetarian; 3, ovo-vegetarian; 4, lacto-ovo vegetarian; 5, other (please refer)].

Anthropometric assessment

Children's weight will be measured on leveled platform scale to the nearest 0.5 kg and height on a wall-mounted stadiometer to the nearest 0.5 cm. Body Mass Index (BMI) (kg/m²) will be calculated by dividing the weight in kilograms by the height in meters squared.

Medical history assessment

Children's medical history will be recorded by asking all the chronic conditions that they may have.

Genotype characterisation

A buccal swap sample will be collected from all children. In specific, standard buccal swab kits will be used to gather DNA sample for sample, as described in Deliverable 3.1.

Metabolome characterisation

For the characterisation of the children's metabolic profile, urine and blood samples will be collected as described in Deliverables 2.2 and 3.1.

Microbiome assessment

Fecal samples from all children will be collected for microbiome analyses. The protocol is described in Deliverable 2.1.

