Beyond the physiological adaptations of HM composition, research has focused on the potential effects of the maternal diet on the HM composition. In an earlier report, HM's composition was found rather constant among mothers of diverse ethnic backgrounds, with different dietary habits [24]. The total fat content of HM has been found to be independent of the mother's diet [25], but responsive to the mother's fatty acids dietary intake [26, 27]. In a recent comprehensive systematic review of 104 observational and interventional studies, HM composition was found to relate to the maternal consumption of fatty acids, fat-soluble vitamins, vitamin B1 and vitamin C intakes [28, 29]. No similar relationships were found for dietary intake of iron, folate, calcium, selenium or proteins [28]. However, more studies are needed to conclude for other nutrients and little is known on how the maternal diet may also affect non-nutritive constituents of the HM, i.e. prebiotics content[30], interactions with gut microbiota [31, 32]. Finally, existing evidence is mainly based on studies on full-term infants; the impact of maternal nutrition on the composition of the HM for the pre-term offspring has not been adequately documented. Thus, it still remains unknown whether dietary advice to the nursing mother could enhance the premature offspring's growth rate, and if so, whether non-nutritive aspects of the HM play any part, or mediate this process.

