3.3.3.1. Measurements

During their stay at the hospital mothers of all three groups will receive nutritional advice based on current knowledge and following the standard protocols of HULAFE.

Measurements concern sociodemographic information, dietary and other lifestyle behaviors, anthropometry, medical history, genotype, metabolome, and microbiome.

Sociodemographic information

Mothers of PT-OMM, PT-DHM and FT-OMM and donors providing the DHM will be asked to self-characterize their annual household income and their family income (ranging from 1, 0-4,999 € to 9, over 50,000 €), whether they have active health insurance (yes/no), their employment status (1, unemployed; 2, employee in private sector; employee in public sector; 3, self-employed; 4, working without pay in family business; 5, on leave (excluding maternity); 6, pensioner), whether they are on maternity leave (yes/no) and their marital status (1; married, 2; unmarried/co-habiting, 3; single parent, 4; divorced or separated, 5; widowed) [33, 34]. Education level will be described by the number of years

H2020 Contract No 818110

on education, while information about the number of people living with the family and in the household will also be included. Maternal or donor's age and origin will be recorded (1; White, non-Hispanic; 2; Black, non-Hispanic; 3, Hispanic; 4, Asian; 5, other).

Dietary assessment

Mothers of PT-OMM, PT-DHM, and FT-OMM will complete a validated semi-quantitative food frequency questionnaire (FFQ) [35]. FFQ will be administered by trained personnel and it comprises 69 questions on the consumption of foods that are commonly eaten by various populations throughout a year, including dairy products, cereals, fruits, vegetables, meat, fish, legumes, added fats, alcoholic beverages, stimulants and sweets. Using a 6-grade scale ("never/rarely", "1-3 times/month", "1-2 times/week", "3-6 times/week", "1 times/day", "≥2 times/day"), participants will be required to indicate the absolute frequency of consuming a certain amount of food, expressed in g, milliliters or in other common measures, such as slice, tablespoon or cup, depending on the food. The previous month will be set as the timeframe.

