3.3.6. Statistical analysis

Associations between mothers' diet and HM composition will be examined with linear regression models. Associations with the macro- and micro-nutrients of the mothers' diet as the independent variable and HM macro- and micro-nutrient composition as dependent variable using prematurity, age and years of education as covariates, will also be examined using linear regression models. The analyses will be repeated separately from the groups of PT-OMM and FT-OMM. Furthermore, linear regression models will be performed with the HM macro- and micro-nutrient composition as the independent

variables and weight, length, cranial perimeter and number of diseases as the dependent using prematurity, age, years of education etc., as the covariates. The analyses will be repeated separately for the groups of preterm and full-term infants. Finally, composition of DHM in terms of nutrients and microorganisms content will be compared before and after pasteurization/storage using Student's t-test or Mann-Whitney test. The analyses will be performed by using STATA software (STATA Corp LLL, College Station, TX, USA).

Finally, additional statistical analysis with the view of deriving additional insights and influences in personalised nutrition will be presented in D2.5.

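### Study II relates milk nutrients to maternal intake measured from food and drink only; vitamin, mineral and fish-oil supplements are neither recorded nor excluded

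*Protocol*

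**What the plan says.** Objective (a) of Study II (Protocol 3.2) is the association between maternal diet and milk composition, and how prematurity affects it. Section 3.3.6 serves this objective with linear regressions: "Associations with the macro- and micro-nutrients of the mothers' diet as the independent variable and HM macro- and micro-nutrient composition as dependent variable". The only covariates it names for them are prematurity, age and education. They are repeated separately in the PT-OMM and FT-OMM groups.

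Maternal intake has two sources:

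- The food frequency questionnaire (FFQ), of which 3.3.3.1 says "it comprises 69 questions on the consumption of foods that are commonly eaten by various populations throughout a year". The full list in Appendix 5.2 contains foods and beverages only.
- The 4-day record returned at month 1 (3.3.4.1), "in which they will have recorded all foods and drinks consumed for three consecutive weekdays and one day of the weekend".

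Two other Study II items come near to supplements. The exclusion criteria in 3.3.2 include "Mother consuming probiotics". The maternal medical history in 3.3.3.1 includes use of medicines, with no dose and no stated link to nutrient intake.

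Study I treats supplements differently. Its exclusion criteria (2.3.2) list "Use of dietary supplements, including multivitamins, fish oil capsules, minerals, and trace elements" as an item separate from medicines, and 2.3.3.1 adds that "intake of dietary supplements (e.g. vitamins) will be recorded".

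**The concern.** The Study II background (3.1) reports from a systematic review that "HM composition was found to relate to the maternal consumption of fatty acids, fat-soluble vitamins, vitamin B1 and vitamin C intakes". Products of the kind that Study I names, such as multivitamins and fish oil, can supply these nutrients. A mother who takes one has a source of the exposure nutrient that neither instrument sees and that no covariate in 3.3.6 represents.

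At stake is the micro-nutrient and fatty-acid part of objective (a). An unmeasured source can hide a real association between diet and milk. If takers eat differently from non-takers, it can also distort the food coefficient. If mothers of preterm and term infants differ in use, it can distort the prematurity effect. A later statistical analysis plan cannot adjust for data that were not collected.

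**Working it through.** **Text check.** The plan states no figure on this point, so there is none to reproduce. The relevant places compare as follows.

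| Item | Study I | Study II |
|---|---|---|
| Supplements excluded | Yes (2.3.2) | Probiotics only (3.3.2) |
| Supplements recorded | Yes (2.3.3.1) | Not mentioned in section 3 |
| Medicines | Separate exclusion item (2.3.2) | Use recorded, no dose (3.3.3.1) |
| Supplement term in the diet-milk model | Not applicable | None (3.3.6) |

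Because 2.3.2 lists medicines and supplements as two items, the medicines entry in 3.3.3.1 cannot be relied on to capture supplements. It might catch a prescribed product.

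**Illustration of size.** Every input here is assumed, except the group sizes (25 per group, so 50 mothers in PT-OMM plus FT-OMM). Let total intake be T = F + S. Food intake F has SD 1, and a share p of mothers gets s food-SDs of the nutrient from a supplement. Let the true correlation of T with the milk nutrient be 0.40.

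*Case 1: use independent of food intake.* The variance of S is p(1−p)s², so

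observed r = 0.40 / √(1 + p(1−p)s²).

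Power uses Fisher's z, two-sided 5%: Φ(atanh(r)·√(n−3) − 1.96). With p = 0.5, p(1−p) = 0.25:

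| s | Divisor | Observed r | Power, n = 50 | Power, n = 25 |
|---|---|---|---|---|
| 0 | 1 | 0.40 | 83% | 51% |
| 1 | √1.25 | 0.36 | 73% | 42% |
| 2 | √2 | 0.28 | 51% | 28% |
| 3 | √3.25 | 0.22 | 34% | 18% |

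With p = 0.2 or 0.8, p(1−p) = 0.16. Observed r is then 0.37, 0.31 and 0.26, and power at n = 50 is 76%, 60% and 43%. The slope on food intake stays unbiased in this case. The power figures count each mother once and ignore covariates. Since the FFQ and own mother's milk are collected at several visits, they show the direction of the loss and do not predict the study's power.

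*Case 2: use related to food intake.* Let takers' mean food intake differ from non-takers' by δ. The food slope is multiplied by 1 + cov(F,S)/var(F). With overall food SD 1, this is 1 + s·p(1−p)·δ. For p = 0.5:

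- δ = +0.5 gives 1.125, 1.25 and 1.375 for s = 1, 2 and 3.
- δ = −0.5 gives 0.875, 0.75 and 0.625.

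If SD 1 is instead taken as the SD within takers and within non-takers, the multipliers are 1.12 to 1.35 and 0.88 to 0.65.

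The two cases are alternatives. The power figures of Case 1 must not be combined with the slope bias of Case 2.

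**The case against.** The strongest reply is that the stated exposure is the mother's diet. On that reading, food-based intake and the MedDietScore are correct measures, and replacing them with food plus supplement would change the question. This stands against the stronger reading, that intake is wrong for every mother who takes a supplement. It does not remove the gap: supplements then become an unmeasured determinant of milk composition, and the model still needs them as a covariate.

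Other points also limit the concern:

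- A reader might infer that associations are exaggerated. The documents do not support a direction. Bias requires use to be related to food intake or to group, and it can then go either way.
- The sociodemographic dictionary (Appendix 5.1) has no supplement item, but it also lacks the one that Study I plainly records. Its silence proves little. The 4-day record form is not reproduced, so its instructions cannot be seen. The point rests on what section 3 and the FFQ list state.
- The scope is narrow. Objectives (b) and (c) do not use maternal intake, and macro-nutrients other than fatty acids are probably little affected.
- Donors complete the FFQ (3.3.4.1), but no diet-milk regression in 3.3.6 is stated to use donor intake.

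**Conclusion.** The gap is real for micro-nutrients and fatty acids in the objective (a) regressions. As written, Study II does not capture supplement intake that can supply the nutrients its own background says milk responds to, while Study I controls for such intake twice. The certain consequence is that total intake is understated in any mother who takes such a product. What follows depends on the pattern of use: lost correlation and precision if use is unrelated to food intake, and bias of unknown sign if it is related to food intake or prematurity group.

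The size cannot be fixed from the documents, which give neither prevalence nor dose. The fall from 0.40 to about 0.36 to 0.22 holds only if half the mothers take 1 to 3 food-SDs independently of food intake. The point does not show that food-only intake is an invalid measure of diet, nor that the study's associations will be inflated.

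**What to change.** In 3.3.3.1 and 3.3.4.1, record each mother's supplement product, dose and frequency with every FFQ and on the 4-day record. The Study I text says only that intake is recorded, so product, dose and frequency need to be spelled out.

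In 3.3.6, run the micro-nutrient and fatty-acid diet-milk regressions with supplement intake of the nutrient as a covariate, keeping food intake as the diet exposure. Add total intake (food plus supplement) as a companion or sensitivity analysis. Recording for donors is optional unless an analysis of donor intake is added.

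The cost is one short questionnaire item per visit, entry of product contents and a small amendment. No extra visits, samples or participants are needed. The change has to be in place before the first maternal assessment to cover all mothers.
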